10.5 Interim Analysis

No interim analysis of efficacy is planned.

10.6 Subgroup Analyses

The primary analysis (ECR) results will be assessed separately across PORT Risk Class, use of prior antibiotics and geographic region stratum by treatment group for both the as randomized strata and the actual strata as indicated on the eCRF. For each PORT Risk Class stratum, prior antibiotic stratum and each geographical region stratum, a 2-sided 95% CI for the observed difference in the Early Clinical Success rates will be calculated for the ITT population. If a clinically meaningful treatment group-by-PORT Risk Class, treatment group-by-prior antibiotic use, or treatment group-by-geographical region result in the opposite direction of the overall result is noted, an inferential test may be performed as a descriptive statistic.

Results of the overall assessment of Clinical Response at the PTE Visit (based on the investigator's assessment at the EOT and PTE Visits) will also be assessed across PORT Risk Class, use of prior antibiotics, and geographic region strata by treatment group for both the as randomized strata and the actual strata as indicated on the eCRF. Separately for each PORT Risk Class stratum, use of prior antibiotics stratum and for each geographical region stratum, 2-sided 95% CIs for the observed difference in clinical response in the ITT and CE-PTE populations will be calculated. If a clinically meaningful treatment group-by-PORT Risk Class, treatment group-by-prior antibiotic use, or treatment group-by-geographical region result in the opposite direction of the overall result is noted, an inferential test may be performed as a descriptive statistic.

11 SAFETY AND TOLERABILITY

All safety analyses will be conducted in the Safety population. Subjects who receive the wrong test article for their entire course of treatment will be analyzed in the group based on the drug received. If a subject receives both omadacycline and moxifloxacin, the subject will be analyzed in the omadacycline arm regardless of the amount of omadacycline received or the randomized treatment assignment. Safety parameters include adverse events (AEs), vital signs, electrocardiogram (ECG) parameters, and clinical laboratory parameters.

11.1 Adverse Events

Verbatim descriptions of AEs will be coded using Version 17.1 or higher of MedDRA. Summary tables will be provided for all treatment-emergent adverse events (TEAEs) but all AEs will be provided in a listing. A treatment-emergent AE is defined as any AE that newly appeared, increased in frequency, or worsened in severity on or after the initiation of active test article. An AE is considered treatment emergent if the AE start date and time is on or after the start date and time of the first infusion of active test article. If time of the AE is missing and it occurred on the same date as the first infusion of active test article, the AE will be defined as treatment emergent. If the start date of the AE is partial or missing and it cannot be determined if the AE occurred prior to or after the first dose of test article, the AE should be defined as treatment emergent.

Subjects assigned to the moxifloxacin arm receive placebo as their first infusion of test article. The AEs of subjects who experience an AE during this placebo infusion and prematurely discontinue from test article prior to receiving moxifloxacin, will only be presented in a listing.

An overall summary of AEs will include the number of subjects who experienced at least one AE of the following categories: any AE, any TEAE, any drug-related TEAE, any severe TEAE, any serious TEAE, any drug-related SAE, any serious TEAE leading to death, any TEAE leading to premature discontinuation of test article, any TEAE leading to premature discontinuation from the study, any TEAE leading to dose interruption of test article, and any serious TEAE leading to premature discontinuation of test article.

The number and percentage of subjects reporting a TEAE in each treatment group will be tabulated by system organ class and preferred term; by system organ class, preferred term, and severity (mild, moderate, and severe); and by system organ class, preferred term, and relationship (unrelated or related to test article). The incidence of TEAEs will be summarized by preferred term and treatment group, sorted by decreasing frequency in the omadacycline group, for all TEAEs, related TEAEs, serious TEAEs, and TEAEs leading to study drug discontinuation. The number and percentage of subjects reporting a TEAE of infusion site reaction (based on the MedDRA higher level term) will be tabulated by treatment group, preferred term and severity (mild, moderate, and severe). The incidence of serious TEAEs, TEAEs leading to premature discontinuation of test article, and TEAEs leading to a dose interruption of test article will be summarized by system organ class and preferred term. For all analyses of TEAEs, if the same AE (based on preferred term) is

reported for the same subject more than once, the AE is counted only once for that preferred term and at the highest severity and strongest relationship to test article.

The table of all TEAEs occurring while on treatment and post-treatment will be summarized by system organ class and preferred term for those subjects who received at least 4 days of iv test article. TEAEs occurring (ie, with a start date and time) during the time period subjects are on treatment, and separately for the time period subjects are on iv and po test article will be summarized by system organ class and preferred term.

In addition, all AEs (including non-TEAEs), serious TEAEs, TEAEs leading to discontinuation of test article, and TEAEs leading to dose interruption of test article will be provided in listings by treatment group, study site, subject, verbatim term, MedDRA system organ class and preferred term, start and end date, seriousness flag, severity, relationship to test article, relationship to study protocol, action taken with test article, non-test article action taken and outcome.

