6 DEFINITIONS

Term	Definition
Regulation	The term regulation refers to all applicable regulations, laws, and guidelines. The regulations may be international, national, or local and may include but are not limited to the Code of Federal Regulations (CFR); the Good Clinical Practice (GCP); Consolidated Guideline (Canada); the International Conference on Harmonisation Guideline for Good Clinical Practice; the Therapeutic Goods Administration Annotated International Conference on Harmonisation Guidelines (Australia); the World Medical Association Declaration of Helsinki: Ethical Principles for Medical Research Involving Human Subjects.
Regulatory agency	The term regulatory agency refers to all health and regulatory agencies with oversight responsibility for the study. These may be international, national, or local and may include but are not limited to the Australian Therapeutic Goods Administration (TGA), the Canadian Health Products and Food Branch (HPFB), the European Agency for the Evaluation of Medicinal Products (EMEA), the United States (US) Food and Drug Administration (FDA).
Sponsor	The term sponsor refers to, but is not limited to the sponsor listed in the front of this document and any contract research organization that is being used for the study.
Test article	Any study drug, device, biologic agent, or comparator (including placebo) used in sponsor studies. For test article accountability, this term applies to the above articles when they are required by the protocol and supplied (shipped) by the sponsor (including diluents such as normal saline [NS] for injection).
Adverse Event	An adverse event (AE) is any untoward, undesired, or unplanned event in the form of signs, symptoms, disease, or laboratory or physiologic observations occurring in a person given a test article or in a clinical study.

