14.3.1.1 Intravenous Treatment Phase (Test Article)

The iv treatment phase (minimum of 3 days, 4 doses) will follow a double-dummy design with placebo infusions matched to active omadacycline and moxifloxacin infusions as shown in [Table 1](#). Infusions of omadacycline and matched placebo will be administered continuously over approximately 30 minutes. During the first 24 hours of iv treatment, subjects on the moxifloxacin treatment arm will receive a placebo infusion to match the $t = 12$ h infusion in the omadacycline arm as shown in Table 1.

Infusions of moxifloxacin and matched placebo will be administered continuously over approximately 60 minutes. All infusion start and stop times are to be recorded in source documents and on the eCRF. Because the color of the test article and placebo infusions are different, all infusion bags and iv tubing will be covered with materials provided by the sponsor (as described in the Pharmacy Manual) so that subjects and blinded study personnel will not know the identity of the test article being administered. Subjects in each study arm will receive the same infusion volumes with the same blinded administration instructions. All iv infusions will be administered by qualified blinded personnel. If gravity administration is not the standard of care then an infusion pump may be used. If an infusion pump is used then a potentially unblinded administrator will be required (see [Section 25.3](#)). All subjects should remain in a hospital setting while on iv test article (for a minimum of 3 days, 4 doses). Thereafter, subjects should not be discharged from the hospital prior to completion of protocol specified assessments, except in circumstances where the Principal Site Investigator has clearly identified that sufficient resources and processes are available to complete all study procedures as defined in the protocol

and the sponsor has reviewed and approved the process for outpatient iv test article administration.

Table 1 Treatment Regimens for IV Test Article

Infusion Regimen ^a	Omadacycline Arm ^{b,c}	Moxifloxacin Arm ^{b,c}
t = 0 h ^d	omadacycline 100 mg in 100 mL NS 250 mL NS placebo	100 mL NS placebo moxifloxacin 400 mg in 250 mL 0.8% saline
t = 12 h	omadacycline 100 mg in 100 mL NS	100 mL NS placebo
t = 24 h ^d	omadacycline 100 mg in 100 mL NS 250 mL NS placebo	100 mL NS placebo moxifloxacin 400 mg in 250 mL 0.8% saline

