22.7.1 Adverse Events

Summary tables will be provided for all treatment-emergent adverse events (TEAEs). A TEAE is defined as an AE with a start date and time on or after the first dose of test article. AEs will be

coded using the Medical Dictionary for Regulatory Activities (MedDRA) and will be summarized by presenting the number and percentage of subjects having each TEAE for each treatment group by system organ class (SOC) and preferred term (PT). Additional tabulations will provide summaries by SOC and PT of subjects experiencing SAEs, severe TEAEs, TEAEs judged to be related to test article, TEAEs leading to discontinuation of test article, TEAEs leading to dose interruption of test article, and TEAEs of special interest.

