6.1.2 Safety Population

The Safety population will consist of all randomized subjects who receive test article (either active or placebo). All safety analyses will be conducted in this population.

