7 CHANGES IN CONDUCT OR PLANNED ANALYSES FROM THE PROTOCOL

The expanded microITT population was added and selected analyses are conducted in this population.

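### SAP 11.1 starts the treatment-emergent clock at the first active infusion, so timed adverse events are captured at least 30–45 minutes later in the moxifloxacin arm, contrary to the protocol and undeclared

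*Combined protocol and SAP*

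**What the plan says.** SAP 11.1 treats an AE as treatment emergent if its onset is "on or after the start date and time of the first infusion of active test article". Its general definition, just before that, is likewise tied to active test article. The section then notes: "Subjects assigned to the moxifloxacin arm receive placebo as their first infusion of test article". It sends to a listing only the AEs of moxifloxacin-arm subjects who have an event during that infusion and stop before any moxifloxacin is given.

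The protocol's rule, in 22.7.1, is different: "A TEAE is defined as an AE with a start date and time on or after the first dose of test article". Protocol Section 6 defines test article as "Any study drug, device, biologic agent, or comparator (including placebo) used in sponsor studies", so the protocol's clock starts with the first bag whatever it contains.

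The denominator is set in SAP 6.1.2: "The Safety population will consist of all randomized subjects who receive test article (either active or placebo"). SAP Section 7, which lists departures from the protocol, has one entry: "The expanded microITT population was added and selected analyses are conducted in this population". The TEAE definition is not mentioned there.

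**The concern.** In a double-dummy trial the two arms receive the same sequence of bags, so background and procedural events (cannula-site complaints, nausea, palpitations from the illness itself) should arise equally and be counted equally. A clock tied to active drug gives up that symmetry, because active drug arrives in the first bag in one arm and in the second bag in the other. Two subjects with the same event at the same minute would be tabulated differently because of their arm.

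The tables exposed are those built on TEAEs: overall incidence by system organ class and preferred term, and the subsets for serious events, related events, infusion-site reactions, discontinuations and dose interruptions. Safety of omadacycline is the first secondary objective listed in SAP 4.2, and these tables are what readers will use to set the arms side by side. Because the change is undeclared, someone who knows only the protocol would misread what the tables count.

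**Working it through.** The plan gives no figure on this point to reproduce. The check compares the two definitions against the infusion schedule.

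**Inputs**
- Bags at t = 0, protocol 14.3.1.1, Table 1. Omadacycline arm: "omadacycline 100 mg in 100 mL NS 250 mL NS placebo". Moxifloxacin arm: "100 mL NS placebo moxifloxacin 400 mg in 250 mL 0.8% saline".
- Order, Table 1 note d: the 100 mL bag runs first and the 250 mL bag second, in both arms.
- Length of the 100 mL bag, Table 1 note b: 30 to 45 minutes.
- Time zero, Table 1 note a: the start of the first infusion, in both arms.
- Gap between bags, g: not stated, so g ≥ 0.
- Randomization: 750 subjects at 1:1, so 750 / 2 = 375 per arm.

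**Step 1: when the window opens.** Let D be the length of the first bag.
- SAP rule, omadacycline: 0 minutes.
- SAP rule, moxifloxacin: D + g, which is at least 30 to 45 minutes.
- Protocol rule: 0 minutes in both arms.

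**Step 2: the same event in each arm.** Take an AE with a recorded onset time inside the first bag.

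| Case | Omadacycline, SAP | Moxifloxacin, SAP | Either arm, protocol |
|---|---|---|---|
| Subject continues treatment | TEAE | Not a TEAE by the start-time rule | TEAE |
| Subject stops during the bag | TEAE, also in the discontinuation table if the AE led to it | Listing only | TEAE |

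In the second row the moxifloxacin subject has received placebo and so belongs to the Safety population. No rule moves that subject to another arm, so I take the subject to remain in the moxifloxacin denominator.

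**Step 3: consistency within the SAP.** The partial-date rule in 11.1 refers to the first dose of test article, without the word active. The vital-sign and ECG baselines in 11.2 and 11.3 are also tied to initiation of test article. So a moxifloxacin-arm heart rate taken while the first bag is still running can be post-baseline when an AE starting at that minute is not treatment emergent. Nor does the SAP exclude placebo infusions in general: an AE during the moxifloxacin arm's placebo infusion at 12 hours counts, because active drug has already been given.

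**Step 4: size, for illustration.** Let r be the fraction of each arm with a timed AE starting in the first bag. The documents do not give r. The gross number counted for omadacycline and not for moxifloxacin is 375 × r:
- r = 0.5%: 375 × 0.005 = 1.9
- r = 1%: 375 × 0.01 = 3.75
- r = 2%: 375 × 0.02 = 7.5

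SAP 11.1 counts each preferred term once per subject. If a fraction q of the affected moxifloxacin subjects has the same term again after active drug starts, the net number is 375 × r × (1 − q), which is smaller. The documents do not give q either.

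**The case against.** The strongest defence is that the choice is deliberate and stated: SAP 11.1 explains the placebo-first sequence and sets a rule for it. Protocol 22.7 analyses safety by treatment actually received, and an event during saline cannot be caused by moxifloxacin. But the treatment-received principle decides which arm a subject is counted in, not when that arm's window opens. Background events in the same minutes do count for omadacycline, so excluding them on one side only does not isolate drug effect.

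Several mitigating points stand:
- An AE with no recorded time on the date of the first active infusion counts in either arm, and so does one whose date cannot be placed. Only timed events are affected.
- An AE that worsens after moxifloxacin starts could qualify under the general definition in 11.1, although the start-time sentence would leave it out. The two are not fully aligned.
- First-bag events in subjects who continue can still appear in the row for any AE, and all AEs are listed.
- In the Phase 2 skin-infection study (protocol 9.1), discontinuation for an AE over the whole course was 0.9% and 1.9%. Stopping during one saline bag should therefore be rare.

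A reader might infer an artefact of 1–3 percentage points, or that the first bag is when infusion events are most likely. The documents support neither. They give no onset rate. Protocol 9.1 puts the Phase 2 heart-rate peak at 4 hours, the most consistent Phase 1 increases in the 2 hours after infusion, and omadacycline nausea and vomiting mainly in the oral phase.

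**Conclusion.** The inconsistency is real and should be corrected. As written, the SAP departs from protocol 22.7.1 without saying so. It makes the TEAE window depend on the arm, with an offset of at least 30–45 minutes for timed events. It also keeps moxifloxacin subjects who have an AE and stop during the placebo bag in the denominator while excluding them from the TEAE counts.

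The size is unknown. The illustration of about 2 to 8 subjects out of 375 rests on an assumed first-bag onset rate of 0.5–2%, equal in both arms, with no later recurrence of the same term. Recurrence reduces it.

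A reader might infer that this compromises blinding, hides harm from omadacycline, or undermines a statistical conclusion. None of these follows. The TEAE flag is an analysis derivation: AEs are collected from consent in both arms and characterised before unblinding. Any distortion raises omadacycline's count relative to moxifloxacin's. No hypothesis, margin or test is planned for AEs. What is affected is the like-for-like reading of descriptive tables, infusion-site reactions and discontinuations among them.

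**What to change.** In SAP 11.1, define treatment emergent as onset on or after the start of the first infusion of any test article, active or placebo, in both arms, matching protocol 22.7.1. Make the same change in the general definition and in the missing-time rule, which also refer to active test article. Delete the listing-only sentence for AEs during the placebo infusion. If the sponsor wants the distinction kept visible, flag AEs with onset before the first active drug in a footnote.

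The cost is SAP wording and about one line of programming. The downside is that a few placebo-period events will appear under moxifloxacin, which the optional flag would make clear.

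The minimum alternative is to declare and justify the active-infusion rule in SAP Section 7 and add a TEAE table using the protocol definition. That discloses the asymmetry but leaves it in the main tables.

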11.2 Vital Signs

Blood pressure (systolic and diastolic), respiratory rate, temperature, and pulse/heart rate will be summarized using descriptive statistics at the following time points: prior to each infusion while the subject is on iv treatment, EOT Visit, PTE Visit, and highest and lowest post-baseline value. Heart rate and blood pressure will be summarized for the following additional time points: for the first 3 doses of test article, just prior to the first infusion, within 30 to 90 minutes after the start of the first infusion and 3.5 to 5.5 hours after the start of the first infusion. Descriptive statistics of the change from baseline to each post-baseline time point and the highest and lowest post-baseline value will also be provided. Baseline is defined as the value closest to but prior to the initiation of test article administration. If no value is available prior to the initiation of test article administration, a value within 2 hours after initiation of test article administration.

Post-baseline vital signs will be defined as clinically notable (CN) if they meet the criterion value or both the criterion value and the change from baseline criterion listed in [Table 8](#). The incidence of CN vital signs will be summarized by time point and treatment group, and will be listed and flagged in by-subject listings. The overall post-baseline incidence of CN values for each vital sign parameter, which includes values from unscheduled post-baseline visits, will also be summarized. A listing will also be provided of subjects with a CN vital sign and will list all values for a vital sign noted as CN.

Table 8. Criteria for Treatment Emergent Clinically Notable Vital Signs

Vital Sign Parameter	Flag	Criterion Value	Change from Baseline
Systolic Blood Pressure (mmHg)	High (CH)	≥ 180	Increase of ≥ 20 mmHg
	Low (CL)	≤ 90	Decrease of ≥ 20 mmHg
Diastolic Blood Pressure (mmHg)	High (CH)	≥ 105	Increase of ≥ 15 mmHg
	Low (CL)	≤ 50	Decrease of ≥ 15 mmHg
Heart Rate (bpm)	High (CH)	≥ 120	Increase of ≥ 15 bpm
	Low (CL)	≤ 50	Decrease of ≥ 15 bpm
Temperature (°C)	Low (CL)	<36.0	NA
	High (CH)	>38.0	NA

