14.3.1.2 Switch to Oral Treatment

The decision to switch to po treatment should be made by the investigator. For a subject to be considered clinically stable and meet criteria for transition to a po regimen, they must have the following findings noted in source documents and recorded on the eCRF:

- Temperature \leq 37.8°C (100°F)
- Heart rate \leq 100 beats/minute
- RR \leq 24 breaths/minute
- SBP \geq 95 mm Hg
- Oxygen saturation \geq 90% as measured by pulse oximetry or PaO₂ \geq 60 mm Hg by ABG
- No worsening of CABP symptoms (cough, sputum production, pleuritic chest pain, dyspnea) compared to Screening
- Normal mental status (“absence of confusion” or pre-illness Baseline for subjects who did not have normal mental status before onset of pneumonia)
- Ability to maintain po intake.

Switch to po will NOT be permitted until after the subject has completed at least the first 3 days of iv treatment (after 4 iv doses).

The date and time the investigator confirmed the criteria for the subject's eligibility for po treatment were met and made the decision to switch to po treatment will be recorded on source documents and the information transferred to eCRFs by study site personnel. For subjects that have been switched to po test article and discharged from the hospital prior to study Day 6, visits must be conducted on study Days 4 and 5, while a study Day 6 visit is optional.

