16.1.2 Vital Signs

Vital signs including body temperature, BP, pulse/heart rate, and RR should be recorded prior to each dose while the subject is on iv treatment. Thereafter vital signs should be recorded at all visits, with the exception of the Final Follow-up visit.

- In addition, for the first 3 doses of test article ($t = 0$ hours, $t = 12$ hours, $t = 24$ hours; see **Table 1**) heart rate and BP should be recorded at the following times: just prior to the first infusion, within 30-90 minutes after the start of the first infusion, and again 3.5-5.5 hours after the start of the first infusion.

All vital signs should be captured after 10 minutes \pm 5 minutes of rest while in a non-standing position (supine or semi-recumbent, head of bed from 0° to 90°). Subsequent vital sign measurements should be captured in the same non-standing position.

Systolic and diastolic BP will be measured using an automated validated device, with an appropriately sized cuff.

Pulse will be measured using an automated validated device, when available. If not available, pulse will be measured manually.

In addition to the above, BP and heart rate may be measured whenever clinically indicated at the discretion of the treating physician. Any subject who experiences an AE of non-pleuritic cardiac chest pain, palpitations, or tachyarrhythmia while on study should have an ECG and an evaluation by the investigator (see [Section 16.1.4.1](#)).

Temperature will be obtained using an electronic (rapid reading) device whenever possible.

RR will be determined by observation.

Once the subject is discharged from the hospital, vital signs will be recorded at each return clinical visit by blinded study personnel.

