22.7.2 Vital Signs

The following variables will be analyzed descriptively:

- Vital signs (systolic and diastolic BP, pulse rate, body temperature, RR) including change from Screening by visit
- Clinically notable vital signs (meeting predefined criteria as specified in the SAP) by visit

Subjects with notable vital signs data will be listed.

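### SAP 11.2 has no vital-sign time point for visits on oral drug before End of Treatment, and from dose 5 its pre-infusion summaries cover only subjects not yet switched

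*Combined protocol and SAP*

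**What the plan says.** Protocol v2.0, 16.1.2, has vital signs recorded before each dose during iv treatment, and then: "Thereafter vital signs should be recorded at all visits, with the exception of the Final Follow-up visit". The study flowchart marks them on Days 4, 5, 6, 7 and 10, at End of Treatment (EOT) and at Post Therapy Evaluation (PTE). Day 6 is optional after oral switch and discharge. Day 10 applies only if treatment runs beyond Day 9.

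Protocol 22.7.2 lists for descriptive analysis: "Vital signs (systolic and diastolic BP, pulse rate, body temperature, RR) including change from Screening by visit". It also promises clinically notable (CN) values by visit.

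SAP 11.2 names these time points: "prior to each infusion while the subject is on iv treatment, EOT Visit, PTE Visit, and highest and lowest post-baseline value". It then adds: "Heart rate and blood pressure will be summarized for the following additional time points: for the first 3 doses of test article", namely just before the first infusion, 30 to 90 minutes after its start, and 3.5 to 5.5 hours after its start. Change from baseline follows the same points. For notable values, "The incidence of CN vital signs will be summarized by time point and treatment group", and in addition: "The overall post-baseline incidence of CN values for each vital sign parameter, which includes values from unscheduled post-baseline visits, will also be summarized".

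SAP 7, on departures from the protocol, contains one item: "The expanded microITT population was added and selected analyses are conducted in this population".

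**The concern.** Two things follow from the SAP 11.2 list.

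First, there is a gap. A subject on oral drug has no infusion to be measured before, so a Day 4, 5, 6, 7 or 10 reading has no SAP 11.2 time point unless that visit is also EOT. The by-visit summary promised in the protocol is missing for those days, for values, change from baseline and CN incidence alike.

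Second, there is selection. The pre-infusion series looks like a time course in the Safety population, but after the minimum iv course it follows only those who have not switched. Switching depends on the vital signs themselves. A later mean can therefore move because stable subjects have left, with no change in any individual. If the arms switched at different rates, the arms would also no longer be compared as randomised at those points. Heart rate matters most here, because protocol 9.1 describes a heart-rate effect of omadacycline.

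**Working it through.** The plan states no figure to reproduce, so the main check sets the sections side by side.

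**1. When the series stops covering everyone.** Protocol Table 1 puts doses 1 to 4 at t = 0, 12, 24 and 48 h, all iv. Its footnotes allow the fifth dose (t = 72 h) to be iv or oral, with the first oral dose as early as t = 60 h. Pre-infusion summaries for doses 1 to 4 therefore cover everyone still on treatment. From dose 5 they cover only subjects still on iv.

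**2. How that subset is selected.** Protocol 14.3.1.2 sets the conditions "For a subject to be considered clinically stable and meet criteria for transition to a po regimen". They include temperature at most 37.8°C, heart rate at most 100, respiratory rate at most 24 and systolic pressure at least 95. Four of the tabulated variables thus help decide who stays in the table.

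**3. Whether another SAP rule fills the gap.** SAP 8.6 and its Table 7 assign readings to windows for safety outcomes, but the on-treatment row is simply Day 1 to Day 10. It creates no vital-sign time point. By contrast, SAP 11.4 summarises laboratory values at Days 4, 7 and 10, and SAP 11.3 summarises ECGs at Day 7, whatever the route.

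**4. Share of the course on oral drug at the earliest switch.** For a course of L days with three on iv, the share is (L − 3)/L: 4/7 = 57% for 7 days and 11/14 = 79% for 14 days. These are upper values, since they assume a switch at the first opportunity.

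**5. Denominators (illustration).** With 750 randomised 1:1 there are 375 per arm. If 25%, 50% or 75% switch before dose 5 (assumed), the pre-dose-5 summary holds 375 × 0.75 ≈ 281, 375 × 0.50 ≈ 188 or 375 × 0.25 ≈ 94 per arm, before other losses.

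**6. Selection effect (illustration).** Assume Day 4 heart rate is normal with mean 88 and SD 14. A subject stays on iv if heart rate exceeds 100 or, independently with probability q, for another reason. All of these inputs are assumptions.
- z = (100 − 88)/14 = 0.857, tail probability p = 0.196, normal density φ(z) = 0.276.
- Share remaining on iv: r = p + (1 − p)q.
- Shift in the mean: 14 × φ(z) × (1 − q)/r.
- Share of those remaining with heart rate above 100: p/r.

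| q | Remaining on iv | Mean heart rate | Shift from 88 | Above 100 (all subjects: 20%) |
|---|---|---|---|---|
| 0.15 | 32% | 98.4 | +10.4 | 62% |
| 0.25 | 40% | 95.3 | +7.3 | 49% |
| 0.40 | 52% | 92.5 | +4.5 | 38% |

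The upward direction for heart rate follows from the switch criterion, other things equal. The bpm values depend wholly on the assumed inputs.

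**The case against.** The case for leaving SAP 11.2 alone has real substance.

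- **The known signal is covered.** Protocol 9.1 describes a transient rise over the first 4 hours after dosing, comparable with controls beyond 6 hours. The timed readings at doses 1 to 3 capture that window before any switch is possible. Oral-day visit readings are not timed to the dose and suit that purpose less well. This stands.
- **Other tables cover part of the gap.** SAP 11.3 gives centrally read ECG heart rate, with change from baseline, at Day 7 and EOT regardless of route. SAP 10.4 tabulates stabilisation of each vital sign at 72 to 120 h in the ITT population, roughly Days 4 and 5. Both stand, but in part. The first is heart rate at a single pre-EOT visit. The second is an efficacy proportion, without means, change from baseline or CN incidence.
- **No data are lost.** On-oral readings enter the highest/lowest summaries, overall CN incidence and listings. SAP 11.1 also splits adverse events by iv and oral period. This stands.
- **The restriction is visible, and the SAP may specify methods.** SAP 11.2 does say that the series applies while on iv, and protocol 22 presents its sections as an outline for the SAP to develop. That weakens any charge of concealment. It does not explain why a by-visit commitment disappears without an entry in SAP 7.

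A reader might infer that the oral phase has no heart-rate summary at all, that heart-rate curves will rise after dose 4 by some stated number of bpm, or that the comparison between arms is biased. The documents support none of these. ECG heart rate is summarised at Day 7, the size of any shift cannot be derived without a switch rate, and nothing indicates that switching will differ by arm.

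**Conclusion.** The point holds as a minor defect in descriptive safety reporting. It touches no hypothesis test and leaves the primary analysis alone.

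Two parts rest on the text alone. On-oral readings between the iv phase and EOT have no SAP 11.2 time point, contrary to protocol 22.7.2 and undeclared in SAP 7. And from dose 5 the pre-infusion summaries describe a post-randomisation subset chosen partly on heart rate, respiratory rate, systolic pressure and temperature. Later means and CN rates may be shifted by that selection. The documents do not allow the amount to be estimated; the shift of 4.5 to 10.4 bpm above shows only what one set of assumed inputs would give. Distortion between arms would further require differential switching.

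**What to change.** In SAP 11.2, add summaries of values, change from baseline and CN incidence at each scheduled visit: Days 4, 5 and 7, Days 6 and 10 labelled as subsets, EOT and PTE. Include every Safety subject with a reading, irrespective of route. Where a day has several readings, the SAP 8.6 rule (closest to the start of the dose) already selects one.

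Keep the pre-infusion summaries, but label those from dose 5 onward *subjects still on iv*. Deleting them is unnecessary and would lose information on longer iv treatment.

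The cost is SAP wording and a few more table pages; the readings are already collected. The limitation to state is that oral-day readings are not timed to the dose.
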